4.4. Research Design

This will be a retrospective analysis of a prospective observational cohort using The CorEvitas RA Registry. This study will describe demographic and clinical characteristics of adult patients with RA initiating tofacitinib with a history of RTX use. This study will also describe changes in clinical and patient reported outcomes over time. The index date will be defined as the date of tofacitinib initiation at or after enrollment in the registry; initiation is defined as first ever use of tofacitinib.

4.4.1. Data Source

The CorEvitas RA Registry is an ongoing longitudinal clinical registry that was established in 2001. Longitudinal follow-up data is collected from both patients and their treating rheumatologist during routine clinical encounters using the CorEvitas RA Registry questionnaires. These questionnaires collect data on patient demographics, disease duration, medical history (including all prior and current treatments for RA), smoking status, alcohol use, cannabis use, disease activity, patient reported outcome measures, disease characteristics, comorbidities and adverse events, infections, hospitalizations, and other targeted safety outcomes. Blood collection, endoscopy and other diagnostic tests are not required for participation; however, relevant standard of care laboratory and imaging results are reported when available.

The registry currently (as of 12 2021) includes 211 private and academic active clinical sites with over 910 physicians throughout 42 states in the U.S. This registry collects data from both the physicians and the patients at the time of a regular office visit. The registry has enrolled over 57,543 patients with RA. The collection of data from The CorEvitas RA Registry represents over 225,180 patient years of data. Structured clinical data is available in this Registry (e.g. disease activity scores, comorbidities, imaging results, patient-reported outcomes data, etc.) that is not available in claims databases.

To be eligible for enrollment into The CorEvitas RA Registry, a patient must satisfy all of the inclusion criteria and none of the exclusion criteria listed below.

Registry Inclusion Criteria

The patient must:

1. Be at least 18 years of age
2. Be able and willing to provide written consent for participation in the registry as well as Personally Identifiable Information (PII) that includes Full Name and Date of Birth at a minimum.
3. Have been diagnosed with RA by a rheumatologist.
4. Meet at least one of the following criteria:
 - a. Currently receiving an Eligible Medication* that was started within 365 days of the Enrollment Visit.

- i. A temporary interruption of an Eligible Medication* is allowed if the interruption in treatment lasted <180 days.
- b. Prescribed or receiving the first dose of an Eligible Medication* on the day of the Enrollment Visit.
- c. Diagnosed with RA within 365 days of the Enrollment Visit regardless of treatment regimen (“Early RA”).

* Eligible Medications are biologics, biosimilars, and JAK-inhibitors FDA-approved for the treatment of RA. Prior use of an Eligible Medication does not exclude a patient from enrollment.

Registry Exclusion Criteria

The patient must not:

- 1. Have a diagnosis of Juvenile idiopathic arthritis (JIA), Psoriatic arthritis (PsA), Spondyloarthritis (SpA), Ankylosing spondylitis (AS), Systemic lupus erythematosus (SLE), or any other form of autoimmune inflammatory arthritis.
- 2. Be starting *only* a non-eligible medication, unless the patient was diagnosed with RA within 365 days of the Enrollment Visit. Non-eligible medications include csDMARDs – for example methotrexate, sulfasalazine, leflunomide, etc. - and including prednisone.
- 3. Be participating in or planning to participate in a double-blind randomized clinical trial of an RA drug. Of note, concurrent participation in another observational registry or open-label Phase 3b/4 trial is not excluded.

Data Included in this Study

Data from The CorEvitas RA Registry as of 28, February, 2022 or the latest data available as of the time of statistical analysis plan (SAP) approval will be used for this study. The study will include visits from 06 November 2012, to the end of data collection.

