9.2.1. Inclusion Criteria

Patients must meet all of the following inclusion criteria to be eligible for inclusion in the study:

Objective 1 Inclusion Criteria:

- Enrolled in the CorEvitas RA Registry and initiated tofacitinib on or after November 2012.
- Initiate tofacitinib (defined as first ever use of tofacitinib) at Registry enrollment visit or at a Registry follow-up visit after November 2012.
- Have prior use of rituximab.
- Have Clinical Disease Activity Index (CDAI) measured at baseline.

Objective 2 Inclusion Criteria:

- Enrolled in the CorEvitas RA Registry and initiated tofacitinib on or after November 2012.

- Initiate tofacitinib (defined as first ever use of tofacitinib) at Registry enrollment visit or at a Registry follow-up, after November 2012.
- Have prior use of rituximab.
- Have CDAI measured at baseline and appropriate follow-up visit.
- Have any of the following:
 - a. A 6-month follow-up visit with persistent use of tofacitinib.
 - b. A 6-month follow-up visit with a tofacitinib discontinuation occurring prior to the 6-month visit, with no new biologic systemic drug used prior to the 6-month study visit.
 - c. A study visit at or prior to the 6-month window with a tofacitinib discontinuation occurring at the study visit.
 - d. (Sensitivity analysis only) Any tofacitinib discontinuation prior to the 6-month study window.

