4.4.2. Study Population of Interest

The primary analysis (Aim 1) will include patients that initiated tofacitinib at or post enrollment into the Registry and after tofacitinib approval, and who have any prior use of RTX. The secondary analysis (Aim 2) will include the subset of patients from the primary analysis who also have a 6-month follow-up visit (as defined below) after tofacitinib initiation with clinical and patient reported outcomes.

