4.4.3. Time Period Definitions

The CorEvitas RA Registry is an observational registry and therefore collects patient and physician data at patient clinical visits with the rheumatologist. Unlike clinical studies, visits are not timed at exact uniform time periods. Thus, time period definitions for the current study need to accommodate this unique feature of observational registries.

“Index visit” is defined as the visit when tofacitinib was initiated, i.e. first ever use of tofacitinib. Only initiations at or after enrollment into the Registry are included.

A “6-month” follow-up is defined as a clinical visit to the rheumatologist 3 to 9 months from the enrollment visit in accordance with the Registry protocol.

4.4.3.1. *Initiations between visits*

If tofacitinib is initiated between visits, then baseline variables from the visit prior to the initiation of tofacitinib will be used, as long as the prior visit occurred within four months of the tofacitinib start date. Initiations that occur between visits and where the prior visit is greater than 4 months from the initiation will be excluded.

4.4.3.2. *Multiple visits in the same time window*

Given the observational nature of the data, it is possible for patients to have more than one visit that falls within a given follow-up period’s allowed time window. For example, a patient might have a visit with outcomes collected at 5 months and then 9 months, both of which would qualify as a “6-month” visit. In that case, the latest visit will be chosen as the “6-month” follow-up since we would like to consider the longest follow-up possible. The exception to this rule is if values for the primary outcome are unavailable for the latest visit, in which case the first visit will be used instead.

4.4.3.3. *Discontinuations prior to follow-up*

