6. LIST OF FIGURES, TABLES AND APPENDICES

Figure 1. Selection of eligible population

Table 1: Patient Demographics and Clinical Characteristics at Index Visit, Primary Cohort and Subset with 6-month Visit (Secondary analysis cohort)

Table 2: Reasons for Discontinuation of Rituximab among Patients who Discontinued at or After Enrollment in the Registry

Table 3: Change in Outcomes from Baseline to 6months Follow-up

Appendix A: Detailed Definitions of Disease Activity Measures and Patient Reported Outcomes in The CorEvitas RA Registry

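### SAP 4.4.1 applies the 06 November 2012 date to all visits; read literally, this conflicts with the rituximab stop-reason population and the four-month baseline look-back

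*SAP*

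**What the plan says.** SAP 4.4.1, under Data Included in this Study, names the Registry data cut (28 February 2022, or the latest available at SAP approval) and then adds: "The study will include visits from 06 November 2012, to the end of data collection". The sentence is about visits. It makes no exception for medication history or baseline.

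Elsewhere the date limit belongs to the start of tofacitinib. Protocol 9.2.1 has "Enrolled in the CorEvitas RA Registry and initiated tofacitinib on or after November 2012", and SAP 4.4.2 requires a start after tofacitinib approval in patients "who have any prior use of RTX", with no date limit on the rituximab.

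Three other parts of the SAP bear on visits before the cut:

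- **Registry age (4.4.1).** The source is an "ongoing longitudinal clinical registry that was established in 2001".
- **Rituximab variables (4.4.6.6 and Table 2).** The SAP asks for duration where available, line of therapy, year of stopping and reason for stopping. Table 2 is titled "Reasons for Discontinuation of Rituximab among Patients who Discontinued at or After Enrollment in the Registry".
- **Between-visit starts (4.4.3.1).** The previous visit serves as baseline "as long as the prior visit occurred within four months of the tofacitinib start date".

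**The concern.** A limit on tofacitinib start dates has been written as a limit on visits. A programmer who builds the extract from SAP 4.4.1 would discard every Registry visit before 06 November 2012. One who works from 4.4.3.1, 4.4.6.6 and the Table 2 title would keep some of them. The two could produce different denominators for Table 2 and for the stop-reason rows of Table 1, and a few different baselines.

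The literal rule would discard stops that the Registry recorded during follow-up, which do not depend on recall of treatment before enrollment. The loss would follow enrollment date, so it would not be random. SAP 4.4.8 expects little missing data, and the limitations in SAP 4.5.2 mention recall but no cut in the visit history. A reader of Table 2 would therefore not be warned.

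**Working it through.** The plan is descriptive and has no sample-size formula to reproduce. Its feasibility split in SAP 4.4.9 is consistent: 8 + 365 = 373; 8/373 = 2.1%; 365/373 = 97.9%. The rest is a comparison of rules and some calendar arithmetic.

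**1. Stop reasons**

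| Rule | Lower limit |
|---|---|
| SAP 4.4.1, visits used | 06 November 2012 |
| SAP 4.4.6.6 and Table 2, rituximab stops | the patient's own enrollment, possible from 2001 |

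For a patient enrolled on or after 06 November 2012 the two limits cannot conflict. For an earlier enrollee they can. Suppose a patient enrolls in 2008, stops rituximab at a 2010 visit where the reason is recorded, and starts tofacitinib in 2014. This patient meets the Table 2 definition, but the visit that holds the reason is outside the SAP 4.4.1 window. The SAP does not say that reasons are repeated at later visits. The stop year may or may not be recoverable from treatment history taken later; the documents do not settle it.

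The documents give no count of stops between enrollment and 06 November 2012, so the number affected cannot be computed.

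**2. Baseline look-back**

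Inputs: visit cut 06 November 2012 (SAP 4.4.1); look-back of four months (SAP 4.4.3.1); 390 initiators at the 31 March 2021 cut (SAP 4.4.9).

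- Earliest visit that can serve as baseline: 06 November 2012 − 4 months = 06 July 2012. Visits from about 06 July to 05 November 2012 are allowed by 4.4.3.1 and excluded by 4.4.1.
- Last start that can be affected: 06 November 2012 + 4 months = 06 March 2013, a span of 120 days.
- Share of the accrual period: 06 November 2012 to 31 March 2021 is 3,067 days, and 120/3,067 = 3.9%. To 28 February 2022 it is 3,401 days, and 120/3,401 = 3.5%.
- Under uniform uptake, an assumption: 390 × 120/3,067 = 15.3, or about 15 starts in the span.

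Only starts between visits with a previous visit before the cut are affected, so the range is 0 to about 15 of 390. A September 2012 visit followed by a between-visit start in December 2012 would be such a case.

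**3. Protocol boundary**

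In Protocol 9.2.1 the first bullet of each objective includes starts in November 2012. The second refers to a start at the enrollment visit, or at a follow-up, after that month. All criteria must be met, so the status of a November 2012 start is unclear. Only starts in that one month are involved.

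**The case against.** The strongest reply is that the sentence was meant for index and follow-up visits only. The data-cut sentence before it has no lower limit, SAP 4.4.2 ties the limit to starts after approval, and prior rituximab use carries no date restriction. This may well be the intent. But the SAP does not say so, and the literal rule contradicts two of its own definitions, so the reply supports a clarification and does not remove the need for one.

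A reader might go further and infer that eligible patients would be missed. The documents do not support that. The questionnaires collect "medical history (including all prior and current treatments for RA", so rituximab given before the cut can be known from a later visit. The feasibility count is of patients with any rituximab history, and line of therapy was available for about 373 of the 376 with baseline CDAI (373/376 = 99.2%).

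A reader might also infer that the whole rituximab block of Table 1 is truncated and tilted toward recent users. Line, duration and immediate prior use are drug-history variables that later visits may supply. Only the stop reason is explicitly restricted to stops during Registry participation. Assuming some share of the 390 and multiplying would give a number of lost stops, but nothing in the documents supports any particular share.

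Nor is this the core of the primary objective. That objective covers all characteristics at tofacitinib start (SAP 4.4.5.1), and rituximab detail is one group among demographics, comorbidities, disease activity, patient-reported outcomes and other medications.

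On Protocol 9.2.1, it is fair to say that the second bullet's date may qualify only the follow-up visit. The wording still allows both readings.

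**Conclusion.** The point holds in a limited form. As written, SAP 4.4.1 conflicts with the enrollment-based population for rituximab stop reasons and with the four-month look-back in SAP 4.4.3.1. Followed literally, it would drop valid Table 2 entries for patients enrolled before 06 November 2012 whose stop was recorded before that date. It could also drop a few valid early baselines.

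The effect on stop reasons, and possibly stop year, is of unknown size. The baseline effect is small, 0 to about 15 of 390, and rests on the uniform-uptake assumption. Loss of eligible patients is not shown. The conflict should be resolved because it can change a planned table and the correction is simple.

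**What to change.** Replace the sentence in SAP 4.4.1 with wording such as: *Tofacitinib index dates and follow-up visits from 06 November 2012 are included. For included patients, all earlier Registry visits are used for medication history, for the year and reason of stopping rituximab, and for baseline under the four-month rule of Section 4.4.3.1.*

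If earlier visits are deliberately not used, restrict and retitle Table 2 to stops from 06 November 2012, give the stop-reason rows of Table 1 the same restriction, add the restriction to SAP 4.5.2, and state how between-visit starts up to about 06 March 2013 are handled.

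In Protocol 9.2.1, use one index-date boundary in both bullets of both objectives, and match it to the SAP's date.

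The cost is wording in the SAP and the protocol. The Registry predates the cut by about 11 years, so the change needs no new data collection, only use of visits already recorded there.

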4.4.2. Study Population of Interest

The primary analysis (Aim 1) will include patients that initiated tofacitinib at or post enrollment into the Registry and after tofacitinib approval, and who have any prior use of RTX. The secondary analysis (Aim 2) will include the subset of patients from the primary analysis who also have a 6-month follow-up visit (as defined below) after tofacitinib initiation with clinical and patient reported outcomes.

4.4.3. Time Period Definitions

The CorEvitas RA Registry is an observational registry and therefore collects patient and physician data at patient clinical visits with the rheumatologist. Unlike clinical studies, visits are not timed at exact uniform time periods. Thus, time period definitions for the current study need to accommodate this unique feature of observational registries.

“Index visit” is defined as the visit when tofacitinib was initiated, i.e. first ever use of tofacitinib. Only initiations at or after enrollment into the Registry are included.

A “6-month” follow-up is defined as a clinical visit to the rheumatologist 3 to 9 months from the enrollment visit in accordance with the Registry protocol.

4.4.3.1. *Initiations between visits*

If tofacitinib is initiated between visits, then baseline variables from the visit prior to the initiation of tofacitinib will be used, as long as the prior visit occurred within four months of the tofacitinib start date. Initiations that occur between visits and where the prior visit is greater than 4 months from the initiation will be excluded.

4.4.3.2. *Multiple visits in the same time window*

Given the observational nature of the data, it is possible for patients to have more than one visit that falls within a given follow-up period’s allowed time window. For example, a patient might have a visit with outcomes collected at 5 months and then 9 months, both of which would qualify as a “6-month” visit. In that case, the latest visit will be chosen as the “6-month” follow-up since we would like to consider the longest follow-up possible. The exception to this rule is if values for the primary outcome are unavailable for the latest visit, in which case the first visit will be used instead.

4.4.3.3. *Discontinuations prior to follow-up*

For patients who discontinue tofacitinib prior to 6 months window, the clinical or patient-reported outcome (listed in Section 4.4.5.2) will be imputed via last observation carried forward (LOCF), using only registry visits that occur before the discontinuation. Specifically, outcomes observed at a registry visit in the 6-month window will use data collected at that visit with the following exception. Patients that discontinue tofacitinib at a registry visit prior to the six month window will have the outcomes collected at that registry visit carried forward as the outcomes in the 6-month window. A patient that discontinues tofacitinib between registry visits will have the outcomes collected at the registry visit prior to the discontinuation carried forward as the 6-month outcome.

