9.4. Data Sources

The CorEvitas RA Registry is an observational registry and therefore collects patient and physician data at patient clinical visits with the rheumatologist. Unlike clinical studies, visits are not timed at exact uniform time periods. Thus, time period definitions for the current study need to accommodate this unique feature of observational registries.

“Index visit” is defined as the visit when tofacitinib was initiated, ie, first ever use of tofacitinib. Only initiations at or after enrollment into the Registry are included.

A “6-month” follow-up is defined as a clinical visit to the rheumatologist 3 to 9 months from the enrollment visit in accordance with the Registry protocol.

Initiations between visits

If tofacitinib is initiated between visits, then baseline variables from the visit prior to the initiation of tofacitinib will be used, as long as the prior visit occurred within four months of the tofacitinib start date. Initiations that occur between visits and where the prior visit is greater than 4 months from the initiation will be excluded.

Multiple visits in the same time window

Given the observational nature of the data, it is possible for patients to have more than one visit that falls within a given follow-up period's allowed time window. For example, a patient might have a visit with outcomes collected at 5 months and then 9 months, both of which would qualify as a "6-month" visit. In that case, the latest visit will be chosen as the "6-month" follow-up since we would like to consider the longest follow-up possible. The exception to this rule is if values for the primary outcome are unavailable for the latest visit, in which case the first visit will be used instead.

Discontinuations prior to follow-up

For patients who discontinued tofacitinib prior to follow-up and who do not switch to another drug, the clinical or patient-reported outcome value at the follow-up visit will be used. If a patient discontinues and switches to another biologic/tsDMARD, the value at the switch visit, if available, will be used; otherwise, the value will be set to missing.

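### The 6-month window is counted from Registry enrollment instead of tofacitinib start, so as written it shortens Aim 2 follow-up for later starters and excludes those who start 9 or more months after enrollment

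*SAP*

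**What the plan says.** Each document gives one numerical definition of the 6-month visit, and the two agree. In SAP 4.4.3, "follow-up is defined as a clinical visit to the rheumatologist 3 to 9 months from the enrollment visit". In Protocol 9.4 the interval is "3 to 9 months from the enrollment visit in accordance with the Registry protocol".

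The study's time zero is a different date. SAP 4.4 states: "The index date will be defined as the date of tofacitinib initiation at or after enrollment in the registry". Protocol 9.1 says the same. Protocol 9.2.1 accepts a first use of tofacitinib "at Registry enrollment visit or at a Registry follow-up visit after November 2012", with no limit on how long after enrollment that may be.

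The documents use enrollment for entry into the Registry. One of the Registry entry criteria in SAP 4.4.1 reads "Prescribed or receiving the first dose of an Eligible Medication* on the day of the Enrollment Visit". SAP 4.4.3 and Protocol 9.4 define the index visit as a separate term, immediately before the 6-month definition.

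SAP 4.4.2 forms Aim 2 from patients with a 6-month visit after tofacitinib initiation and refers forward to the 4.4.3 definition. SAP 4.4.7.2 also describes the follow-up as coming after initiation and measures change from baseline.

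**The concern.** The enrollment visit and the tofacitinib start are the same date only for patients who start at enrollment. The plan expressly admits later starters. It also expects some patients to have stopped rituximab while in the Registry (SAP Table 2 covers those who stopped at or after enrollment). Anyone who stopped after enrollment and then began tofacitinib has a delay above zero.

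The window decides who enters Aim 2 and when its outcomes are read: change in CDAI, MCID achievement, HAQ, pain, fatigue and discontinuations. If it is applied as written, two patients with identical tofacitinib histories can be treated differently only because one joined the Registry earlier. Some values labelled 6-month would come from visits less than 3 months into treatment. Long-standing Registry members who start late would drop out of Aim 2 altogether.

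**Working it through.** **The plan's own figure.** SAP 4.4.9 and Protocol 9.5 report ~107 patients with CDAI at baseline and 6 months, out of ~376 with baseline CDAI (107/376 = 28.5%). This is an observed count from the 31 March 2021 data cut, so there is no formula to reproduce. It does not show which starting point was used.

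**Inputs.**
- Written window: 3 to 9 months from enrollment (SAP 4.4.3, Protocol 9.4).
- Delay s, in months from enrollment to tofacitinib start: s ≥ 0, no upper limit (SAP 4.4 and 4.4.3, Protocol 9.2.1).
- The follow-up visit must come after the start (SAP 4.4.2).
- Intended window, inferred from SAP 4.4.2 and 4.4.7.2: 3 to 9 months from the start.

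**Formulas.** Subtracting s moves the written window to the time scale of tofacitinib use.
- Written window from start: 3-s to 9-s, keeping only times after the start.
- Longest follow-up since start: max(0, 9-s).
- Share of the intended 6-month-wide window that is covered: max(0, 6-s)/6.
- A visit t months after start (t from 3 to 9) counts only if s + t ≤ 9, that is s ≤ 9-t.

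| Delay s (months) | Written window, months after start | Share of intended window covered |
|---|---|---|
| 0 | 3 to 9 | 100% |
| 1 | 2 to 8 | 83% |
| 2 | 1 to 7 | 67% |
| 3 | above 0, to 6 | 50% |
| 4 | above 0, to 5 | 33% |
| 5 | above 0, to 4 | 17% |
| 6 | above 0, to 3 | 0% |
| 8 | above 0, to 1 | 0% |
| 9 or more | none | 0% |

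At s=6 the two windows meet only at the 3-month point. A visit 3 months after start counts up to s=6, one at 6 months up to s=3, and one at 9 months only at s=0. These are properties of the rule, not shares of patients. For starts between visits the baseline visit may be up to 4 months before the start, so the baseline-to-follow-up interval can be longer than the time since start.

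**Can a late starter enter Aim 2 another way?** From s=9, no. Objective 2 routes a and b in Protocol 9.2.1 need a 6-month visit. Route c needs "A study visit at or prior to the 6-month window with a tofacitinib discontinuation occurring at the study visit", but the window has closed by the first dose. Route d is for sensitivity analysis only and needs a discontinuation before the window.

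**Effect on the LOCF rule.** From s=3 the window opens at or before the first dose, so nobody can discontinue before it opens. The pre-window provision in SAP 4.4.3.3 then cannot apply. Its last sentence, on stopping between visits, may still apply, but SAP 4.4.2 still requires a 6-month visit for entry to Aim 2.

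**Calendar bound.** The Registry "is an ongoing longitudinal clinical registry that was established in 2001". Eligible starts begin in November 2012 (Protocol 9.2.1); for visits, SAP 4.4.1 says "The study will include visits from 06 November 2012, to the end of data collection". Taking 1 November 2012 as the earliest possible start and subtracting 9 months gives 1 February 2012. Anyone enrolled before that date is more than 9 months past enrollment at the earliest eligible start. From 2001 to that date is 10.1 to 11.1 years of enrollment, depending on when in 2001 the Registry opened. This reads the November 2012 date in Protocol 9.2.1 as limiting the start of tofacitinib only, as SAP 4.4.2 does.

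**The case against.** The intended starting point can be recovered from the documents. The index date is tofacitinib initiation, SAP 4.4.2 and 4.4.7.2 place follow-up after it, and the provisions for stopping before the window make sense for every patient only if the window runs from the start. The literal rule also defeats itself: SAP 4.4.3 alone would admit pre-treatment visits as follow-up, and the exclusion from s=9 appears only when it is joined to the condition in SAP 4.4.2. The wording cites the Registry protocol, which is not among the documents, so it may be general Registry wording carried over. Nothing shows that the literal rule was programmed. If most patients started at enrollment, the effect would be small. The November 2012 criterion can also be read as dating enrollment as well as initiation, and the calendar bound would then affect nobody. Aim 2 is secondary and descriptive.

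Most of this stands, and it limits what can be said about the effect on results. It does not repair the text. SAP 4.4.2 sends the reader to the faulty definition, and no other section gives an interval in months. The reference to the Registry protocol gives a programmer reason to follow the phrase as written. Recoverable intent makes the correction uncontroversial, but the correction is still needed.

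**Conclusion.** The concern holds and must be fixed. The only numerical definition of the 6-month visit uses the wrong starting point for every patient who begins tofacitinib after enrollment. As written, follow-up since start is capped at 9-s months, none of the intended window's 6-month width is covered from s=6, and Aim 2 entry is impossible from s=9.

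This rests on two readings: that the enrollment visit means entry into the Registry, as elsewhere in the SAP, and that Aim 2 visits must follow initiation, as SAP 4.4.2 says. No distribution of delays is assumed. The number of patients affected, the effect on the ~107 and the direction of any bias therefore remain unknown. It is also unknown whether the analysis code followed the written rule. Aim 1 does not use the window and is unaffected.

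**What to change.** In Protocol 9.4 and SAP 4.4.3, define the 6-month follow-up as a registry visit 3 to 9 months after the tofacitinib start date (the index date), and say that this also holds for starts between visits. In enrollment time the window becomes s+3 to s+9 months (for example, months 9 to 15 at s=6), so follow-up is 3 to 9 months whatever the delay. Check that the visit-selection code uses this starting point, and state which one produced the ~107.

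The cost is one phrase in each document, a code check and one sentence on the ~107. No new data are needed. Protocol 9.7 says that major changes to primary endpoint definitions go into a protocol amendment. Change in CDAI is the primary outcome of Aim 2, so the correction should be made openly in both documents and not only in the code.
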